4.5 Administration

The instructions below provide a summary of the guidance provided in the rituximab product labeling, which should also be followed for SAIT101; rituximab should be administered according to the local product labeling if it differs from these instructions.

- Day 1 infusion will be administered at an initial infusion rate of 50 mg/hour for the first hour. If no toxicity is seen, the rate may be increased gradually in 50 mg/hour increments at 30 minute (± 5 minutes) intervals, to a maximum of 400 mg/hour (See Appendix 8).
- If the Day 1 infusion is well tolerated, the initial infusion rate for subsequent doses will be 100 mg/hour, increased gradually in 100 mg/hour increments at 30 minute intervals, to a maximum of 400 mg/hour.
- Patients should be closely monitored for the onset of infusion related reactions. If the patient experiences infusion related reaction or any ADR, the infusion should be discontinued, and the severity of the side effects should be evaluated. Medical management for infusion reactions must be instituted as needed. Depending on the severity of the infusion reaction and the required interventions, rituximab may be temporarily or permanently discontinued. (See Section 6.4.6).

Resume infusion at a minimum 50% reduction in rate after symptoms have resolved. The Investigator should wait an additional 30 minutes while delivering the infusion at the reduced rate. If tolerated, the rate may then be increased to the next closest rate on the patient's infusion schedule. (See Table 1 in Appendix 8).

An infusion device capable of administering the study drug with rates varying from as low as 0.2 mL/minute up to 3.3 mL/minute would be suitable. This would be best achieved by a volumetric infusion pump. An in-line filter is not mandatory.

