6.4.6 Infusion Reactions

An acute onset infusion reaction generally occurs within 24 hours of infusion of the study drug. Rituximab can cause severe, including fatal, infusion reactions. Severe reactions typically occur during the first infusion with time to onset of 30 to 120 minutes. Rituximab-induced infusion reactions and sequelae include headache, nausea, fever or chills, dizziness, flush, urticaria, hypotension, angioedema, hypoxia, bronchospasm, pulmonary infiltrates, acute respiratory distress syndrome, myocardial infarction, chest or back pain, ventricular fibrillation, cardiogenic shock, anaphylactoid events, or death. Distinction between infusion reaction and anaphylaxis is necessary.

Medical management (e.g., glucocorticoids, epinephrine, bronchodilators, or oxygen) for infusion reactions must be instituted as needed. Depending on the severity of the infusion reaction and the required interventions, rituximab may be temporarily or permanently discontinued. If the same severe (Grade 3) or above infusion reaction occurs for a second time, the decision to discontinue permanently should be seriously considered. Resume infusion at a minimum 50% reduction in rate after symptoms have resolved (see Appendix 8). Closely monitor patients with pre-existing cardiac or pulmonary conditions.

.Please refer also to Section 6.4.3 (Anaphylactic Reactions) for differential diagnosis with anaphylaxis.

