6. In patients with detectable circulating malignant cells, it is strongly advised that the initial infusion rate be reduced to 25 mg/hour; these patients may experience more frequent and severe transient fever and rigors, shortness of breath, and hypotension.
 7. The exact date and time of start of infusion, end of infusion, any interruptions (stop time, restart time etc.), and total dose administered must be recorded in the patient's eCRF.

Table 1 Recommended Infusion Rates

Day 1 infusion	Dose (mg)	Time (minutes) ^a	Cumulative dose (mg)	Day 8, 15, and 22 infusions	Dose (mg)	Time (minutes) ^a	Cumulative dose (mg)
50 mg/h	50	0-60	50	100 mg/h	50	0-30	50
100 mg/h	50	61-90	100	200 mg/h	100	31-60	150
150 mg/h	75	91-120	175	300 mg/h	150	61-90	300
200 mg/h	100	121-150	275	400 mg/h	(375*BSA)-300	^d	^d
250 mg/h	125	151-180	400				
300 mg/h	150	181-210	550				
350 mg/h	175	211-240 ^b	725				
400 mg/h	(375*BSA)-725	^c	^c				

BSA body surface area in m²

- a Allowed window for infusion rate time at each time point is \pm 5 minutes.
- b Approximately 240 minutes (4 hours) to complete a dose of 725 mg.
- c Total dose and time of infusion will depend on patient's BSA. Total dose is 375 mg/m²; every additional 50 mg above a 725 mg dose will require 7.5 minutes infusion of the 400 mg/mL dose.
- d Total dose and time of infusion will depend on patient's BSA. Total dose is 375 mg/m²; every additional 50 mg above a 300 mg dose will require 7.5 minutes infusion of the 400 mg/mL dose.

If the patient experiences fever and rigors, or any ADR, the antibody infusion should be discontinued, and the severity of the side effects evaluated. If the symptoms improve, the infusion may be continued, initially at one-half the previous rate. The Investigator should wait an additional 30 minutes while delivering the infusion at the reduced rate. If tolerated, the rate may then be increased to the next closest rate on the patient's infusion schedule. For example:

(Example 1) An infusion-related reaction or an ADR at a rate of 50 mg/h → change rate to 25 mg/h → reaction resolved → additional 30 minutes at a rate of 25 mg/h → change back to 50 mg/h

(Example 2) An infusion-related reaction or an ADR at a rate of 300 mg/h → change rate to 150 mg/h → reaction resolved → additional 30 minutes at a rate of 150 mg/h → change back to 200 mg/h.

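### Appendix 8 lets a stopped infusion continue once symptoms improve, and its examples omit the stop; Sections 4.5 and 6.4.6 require that symptoms have resolved

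*Protocol*

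**What the plan says.** Four places in the protocol govern what happens after a reaction during infusion.

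- **Appendix 8, text.** The infusion is first stopped: "If the patient experiences fever and rigors, or any ADR, the antibody infusion should be discontinued, and the severity of the side effects evaluated". The restart condition follows: "If the symptoms improve, the infusion may be continued, initially at one-half the previous rate".
- **Appendix 8, examples.** Example 1 starts from a reaction at 50 mg/h and continues "change rate to 25 mg/h → reaction resolved → additional 30 minutes at a rate of 25 mg/h" before returning to 50 mg/h. Example 2 starts from a reaction at 300 mg/h and continues "change rate to 150 mg/h → reaction resolved → additional 30 minutes at a rate of 150 mg/h" before going to 200 mg/h.
- **Section 4.5.** The stop: "If the patient experiences infusion related reaction or any ADR, the infusion should be discontinued". The restart: "Resume infusion at a minimum 50% reduction in rate after symptoms have resolved".
- **Section 6.4.6.** The same restart condition, with a pointer to the appendix: "Resume infusion at a minimum 50% reduction in rate after symptoms have resolved (see Appendix 8").
- **Section 3.3.1.2.** For infusion-related reactions of Grade 3 or above, there is no same-day restart until every symptom has gone completely, and then at no more than half the earlier rate.

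Section 4.8 names Appendix 8 as the place where the infusion instructions for both study drugs are found.

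**The concern.** The body of the protocol makes resolution of symptoms the condition for restarting. Appendix 8, the working instruction for the people giving the drug, asks only for improvement. Its examples then show drug running before the reaction has resolved. Staff at the bedside are likely to copy a worked example.

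Infusion reactions are an adverse event of special interest here, and Section 6.4.6 notes that they can be severe or fatal. A site using Appendix 8 as written could re-expose a patient who still has symptoms.

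There are also consequences for the data. Appendix 8 asks for stop and restart times to be recorded, and SAP Sections 12.1 and 17.1 summarize dose interruptions and adverse events that led to interruption. A site following the examples has no stop to record, while a site following Section 4.5 does, so similar reactions could be coded differently across about 165 sites. The size of that effect cannot be derived from the documents.

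**Working it through.** No power, alpha or sample-size figure is involved. The check sets the passages side by side.

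| Place | Trigger | Infusion stopped first? | Condition for restart | Restart rate |
|---|---|---|---|---|
| Section 4.5 | infusion-related reaction or any ADR | yes | resolved | reduced by at least 50% |
| Section 6.4.6 | infusion reaction | temporarily or permanently, by severity | resolved | reduced by at least 50% |
| Section 3.3.1.2 | Grade 3 or above | yes | completely resolved | at most half |
| Appendix 8, text | fever and rigors, or any ADR | yes | improved | half |
| Appendix 8, examples | infusion-related reaction or ADR | not shown | none; resolution follows the rate change | half |

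**Trigger.** The wording differs slightly, but Section 4.5 and the Appendix 8 text both cover any ADR, and the examples use in substance the Section 4.5 trigger. The rules therefore apply to the same events and cannot be separated by scope. Appendix 8 sets no grade limit on that sentence, so it also overlaps with the Grade 3 rule.

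**Rate.** Example 1: 25 / 50 = 0.50. Example 2: 150 / 300 = 0.50. Both meet the 50% minimum, so the rate is not in conflict.

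**Restart condition.** Three places require resolution and one accepts improvement. A patient who is better but still symptomatic may be restarted under Appendix 8 and may not under the other three.

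**Order of events.** The examples place resolution after the rate change. Read literally, the rate running before resolution is:

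- Example 1: 25 mg/h / 60 = 0.42 mg per minute
- Example 2: 150 mg/h / 60 = 2.5 mg per minute
- Section 4.5: 0 until symptoms have resolved

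The documents give no symptom duration, so no total dose can be computed.

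**Reach.** 308 patients × 4 infusions = 1,232 planned infusions stand under the rule. Only those with a reaction are affected, and the documents give no rate for these.

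**Precedence.** Section 4.5 says "rituximab should be administered according to the local product labeling if it differs from these instructions", and Appendix 8 allows institutional guidelines to be followed. Neither clause ranks Appendix 8 against Section 4.5, 6.4.6 or 3.3.1.2. A site that waits for resolution complies with all four places; a site that follows Appendix 8 alone may not.

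**The case against.** The strongest reply is that this is one loose word and two badly drawn illustrations, with the stricter rule already stated three times.

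- **The examples may be shorthand** for stepping the rate down and up, and the paragraph above them orders a stop. That is a fair reading, but the stop is still missing from the examples and resolution is still in the wrong place. The improvement condition in the text stands whichever way the examples are read.
- **The routing is weaker than it looks.** The pointer in Section 6.4.6 sits in the same sentence as the resolution rule, and Section 3.3.1.2 refers to Section 4.5. This is true, but Section 4.8 sends sites to Appendix 8 without that warning, and a reader who follows Section 6.4.6 there meets a looser rule.
- **Safeguards exist.** Appendix 8 requires close supervision by an experienced physician. It bars further drug after life-threatening reactions, and it stops the infusion and takes the patient off study if the reduced rate is not tolerated for 30 minutes. These limit the harm. The last one acts only once drug is running again.
- **Actual practice depends on labeling and institutional guidelines** that are not in these documents. This is correct, and for that reason no frequency of harm is claimed.
- **The counts say little about harm.** This also stands: 1,232 is the number of planned infusions, and the rates per minute are unit conversions.

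**Conclusion.** The inconsistency is real and should be fixed. For any ADR, Appendix 8 permits a restart on improvement where Sections 4.5 and 6.4.6 require resolution, and both of its examples omit the stop that its own text orders. A site following Appendix 8 could infuse a patient who is still symptomatic, which the protocol body forbids.

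The risk is bounded. It concerns mainly mild to moderate reactions. It reaches Grade 3 reactions that are not life-threatening only if the site reads Appendix 8 without Section 3.3.1.2. How often it would occur, and how much drug would be given, cannot be stated. Confidence is high that the texts conflict; nothing is asserted about how many patients would be harmed.

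**What to change.** In Appendix 8, replace the sentence that allows continuation on improvement with wording such as:

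> Once symptoms have resolved (for Grade 3 or above, once every symptom has resolved completely; see Section 3.3.1.2), the infusion may restart at no more than half the rate at which the reaction occurred.

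Reorder the examples:

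- **Example 1:** reaction at 50 mg/h → stop infusion → reaction resolved → restart at 25 mg/h → 30 minutes at 25 mg/h → 50 mg/h.
- **Example 2:** reaction at 300 mg/h → stop infusion → reaction resolved → restart at 150 mg/h → 30 minutes at 150 mg/h → 200 mg/h.

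While editing, give the Appendix 8 text the same trigger as Section 4.5. If the sponsor prefers improvement as the condition for mild reactions, Sections 4.5 and 6.4.6 must be amended and the examples corrected all the same.

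The cost is a short text change and a site memo. Sites now working to improvement would pause somewhat longer after mild reactions, by an unknown amount, but Sections 4.5 and 6.4.6 already require that wait. Section 4.3 gives 12 hours of physical and chemical stability at room temperature (after up to 24 hours refrigerated) but advises immediate use on microbiological grounds, so long interruptions should be avoided.

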3.3 Stopping Rules, Withdrawal Criteria, and Procedures

3.3.1 Patient Withdrawal

All patients are free to withdraw from participation in the study at any time, for any reason, specified or unspecified, and without prejudice to further treatment. The criteria for enrollment are to be followed explicitly.

In addition, patients may be withdrawn from study drug and/or from the study in the circumstances outlined below.

Distinction should be made between discontinuation of study drug treatment and withdrawal from the study, and the reason for treatment discontinuation or study withdrawal should be recorded by the Investigator. The Sponsor should be notified promptly when a patient is withdrawn from either study drug treatment or the study.

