3.3.1.1 Withdrawal from Study

Patients may be withdrawn from the study for the following reasons:

- a) The patient is unwilling to continue in the study (i.e., withdraws consent). In this case, no more investigations will be performed. The patient does not have to justify their decision.
- b) The patient is lost to follow-up despite reasonable efforts to make contact with the patient. In this case, all attempts to contact the patient, request to return for visit and information received during contact attempts must be documented in the patient's medical record. In any circumstances, every effort should be made to document patient outcome, the reason for withdrawal, and any unresolved or new AEs.
- c) The Sponsor stops the study (see Section 3.3.2) or closes an individual study site (see Section 3.3.3) due to critical non-compliance with study protocol, ICH-GCP or other applicable regulatory requirements.

Patients who are withdrawn from the study will not be replaced.

Adverse events will be followed up as detailed in Section 6.10. Investigators are encouraged to discuss the patient's case with the Sponsor physician or representative to agree upon appropriate action. For patients who need to be withdrawn from the study early, it is highly

recommended that efficacy assessments are conducted at Week 28. Once a patient is withdrawn from the study, no further assessments can be conducted.

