3.3.1.2 Discontinuation of Study Drug

An individual patient may be discontinued from study drug treatment for the following reasons:

- Prohibited treatment such as any other experimental drug or a concomitant chemotherapy, anticancer hormonal therapy, radiotherapy, or immunotherapy.
- Lack of compliance with protocol (e.g., refusal or inability to adhere to the study schedule or procedures).
- Patients who meet any of the following specific safety discontinuation criteria:
 - Patients who develop severe (common terminology criteria for adverse events [CTCAE] Grade 3 or above) infusion-related reactions, especially severe dyspnea, bronchospasm, or hypoxia, should have the infusion interrupted immediately to receive aggressive symptomatic treatment. In all patients, the infusion should not be restarted on the same day until complete resolution of all symptoms. At this time, the infusion may be initially resumed at the discretion of the Investigator at not more than one-half the previous rate. If the reaction was an anaphylactic reaction, or if the same infusion-related reaction occurs for a second time, the infusion should be permanently discontinued (refer to Section 4.5).
 - Active TB.
 - Invasive fungal infection or opportunistic infection including, but not limited to, listeriosis, legionellosis, or pneumocystis.
 - Hepatitis B virus reactivation or hepatic failure.
 - PML: neurological warning signs include major changes in vision, unusual eye movements, loss of balance or coordination, and disorientation or confusion.
 - Cancer: any new malignant lesion. Patients with basal cell and squamous cell carcinomas of the skin or carcinoma in situ of the cervix uteri that has been excised and cured, may be continued on the study at the discretion of the Investigator. If such carcinomas develop during the study, they may be excised and the patient may continue on the study.
 - Any other AEs which, in the opinion of the Investigator or the Sponsor, could compromise the patient's safety or well-being if they continued to participate in the study.

- Pregnancy in a female participant.

Assessments for patients who discontinue the study drug early

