Patients who discontinue the study drug early for any reason will be required to have efficacy assessments at Week 28, and an early treatment discontinuation visit. If new treatment must be started before the Week 28 assessments, then an early treatment discontinuation visit, including a CT scan (see Table 1), should be performed before the start of the new treatment. Patient who discontinue the study treatment will be followed-up until Week 52 (EOS) for safety and immunogenicity.

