If the patient does not tolerate the reduced rate for at least 30 minutes then the infusion should be stopped and the patient discontinued from the study.

Drug infusions will take place under the close supervision of an experienced physician, and in an environment where full resuscitation facilities are immediately available. Although the study drug will be administered on an outpatient basis, and patients discharged after the infusion in accordance with the normal standard of care for rituximab-containing regimens, patients may be hospitalized for observation at the discretion of the Investigator, and such instances of planned hospitalization will NOT be recorded as a serious adverse event (SAE).

Any drugs that are used to manage hypersensitivity reactions or ADRs, including but not limited to epinephrine, antihistamine, and corticosteroid, should be immediately available in case of emergency.

Attention should be given to the development of anaphylaxis during infusion of the study drug. When an anaphylactic reaction is suspected during infusion of the study drug:

- Discontinue the study drug.
- Apply a tourniquet close to the infusion site in order to slow systemic absorption of the study drug. Do not block artery flow.
- Perform appropriate airway management.
- If required, administer antihistamine, epinephrine, or other drugs.
- Closely monitor the patient and document the observations.

Similarly, in the event of any other life-threatening reaction, including hypersensitivity reaction, renal failure, severe cardiopulmonary event and severe mucocutaneous reaction, the study drug will be discontinued and no additional study drug will be administered.

If extravasation occurs during infusion of the study drug, the infusion must be stopped. Restart the remainder of the infusion either in the area of the same arm that is proximal to the body, or in the other arm. The PK, PD and immunogenicity samples will always be drawn from the opposite arm of the infusion arm.

Following the infusion, the i.v. line should be maintained for medications as needed. If there are no complications after 1 hour of observation, the i.v. line may be discontinued. The i.v. line may not be used for sampling for PK, PD, or immunogenicity.

Institutional guidelines for the administration of rituximab, and the kind of premedication, can be followed. Dose modification is not permitted during this study. Any deviation to the dose will be recorded in the eCRF.

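### Appendix 8 takes a patient who cannot tolerate the reduced infusion rate out of the study, where Sections 3.1 and 3.3.1.2 and SAP 2.2 stop only the drug and keep the patient in follow-up

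*Protocol*

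**What the plan says.** Protocol Appendix 8, after the infusion-rate table, deals with a patient who has fever and rigors, or any adverse drug reaction, and is restarted at half rate. If the reduced rate is not tolerated for at least 30 minutes, "then the infusion should be stopped and the patient discontinued from the study". For anaphylaxis the same appendix says to stop the drug. For other life-threatening reactions it says "the study drug will be discontinued and no additional study drug will be administered". In neither case does it mention study status.

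The main body separates the two kinds of exit:

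- Section 3.3.1: "Distinction should be made between discontinuation of study drug treatment and withdrawal from the study".
- Section 3.3.1.1: "Patients may be withdrawn from the study for the following reasons", followed by three reasons (consent withdrawn, lost to follow-up, sponsor stops the study or closes the site). It adds: "Once a patient is withdrawn from the study, no further assessments can be conducted".
- Section 3.3.1.2 lists reasons for stopping study drug. For severe infusion reactions, "if the same infusion-related reaction occurs for a second time, the infusion should be permanently discontinued". A later bullet covers any other adverse event that could compromise safety.
- Section 3.3.1.2, assessments: "Patients who discontinue the study drug early for any reason will be required to have efficacy assessments at Week 28", together with an early treatment discontinuation visit. Then: "Patient who discontinue the study treatment will be followed-up until Week 52 (EOS) for safety and immunogenicity".

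Protocol 3.1 and SAP 2.2 repeat the last two rules.

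**The concern.** Sections 4.5 and 4.8 send sites to Appendix 8 for infusion instructions, so it is the text in use while a reaction is being managed. Its sentence names the study, and under 3.3.1.1 leaving the study ends all assessments. The main body would keep the same patient in follow-up.

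At stake are data from patients who have just reacted to the product. Safety and immunogenicity are secondary objectives in a biosimilarity trial, and infusion reactions are an adverse event of special interest. Data lost because of a reaction are not lost at random. The instruction also fits poorly with its surroundings: in the same appendix, a life-threatening reaction stops the drug without any instruction to leave the study.

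**Working it through.** **1. The texts side by side**

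| Question | Appendix 8 | Main body |
|---|---|---|
| What is stopped? | Infusion and study participation | Study drug (3.3.1.2); 4.5 and 6.4.6 also speak only of stopping rituximab |
| Week 28 efficacy | Not mentioned | Required after an early drug stop for any reason (3.1, 3.3.1.2, SAP 2.2) |
| Safety and antibodies to Week 52 | Not mentioned | Required (3.1, 3.3.1.2, SAP 2.2) |

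The triggers are not identical. The infusion bullet in 3.3.1.2 concerns reactions of Grade 3 or above, with a permanent stop for anaphylaxis or a second occurrence. Appendix 8 starts from any adverse drug reaction. The bullet on other adverse events, and the rule covering any reason for stopping, still bring the Appendix 8 patient under 3.3.1.2.

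Table 1 footnote c supports the Week 28 assessment and the discontinuation visit, but it is worded for discontinuation after Day 1. Section 6.4.6 says severe reactions typically occur at the first infusion, so that footnote does not clearly cover the commonest case.

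**2. What one literal withdrawal could cost**

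Antibody samples (Table 1; SAP 18.1): Weeks 1, 2, 3, 4, 5, 12, 20, 28, 36 and 52, which makes 10. Samples at infusion visits are taken before dosing.

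- Exit on Day 1: 10 − 1 = 9 lost.
- Exit at Week 4 (Day 22): 10 − 4 = 6 lost.
- If an exit visit supplies one sample: 8 and 5 lost.

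Adverse-event capture (6.8, 6.9): all events to 60 days after the last dose, then related events and those of special interest to end of study (Day 365).

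- Last dose Day 1: up to 60 days of all-event reporting, then 365 − (1 + 60) = 304 days.
- Last dose Day 22: up to 60 days, then 365 − (22 + 60) = 283 days.

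Response: infusions fall on Days 1 to 22 and the first scheduled on-study CT is at Week 12, so no earlier scheduled scan stands in for a lost Week 28 result.

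**3. Power, to see whether it matters**

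Inputs (Protocol 8.4): 154 per arm, 77% response in both arms, margin ±16 points, 95% Newcombe-Wilson interval. Exact enumeration of two binomials with the unstratified interval gives 84.0%, against the stated 83% from 1,000 simulations, so the plan's figure reproduces.

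The documents give no event rate. Exit counts of 1 and 3 are assumptions. Counted as non-responders, responders ~ Bin(154 − k, 0.77) over a denominator of 154. Left out, the denominator is 154 − k.

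| Assumed exits | Counted as non-responders | Left out |
|---|---|---|
| None | 84.0% | 84.0% |
| 1 per arm | 83.7% | 83.7% |
| 3 per arm | 83.2% | 82.7% |
| 3 in one arm only | 81.6% | 83.2% |

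One patient moves an arm's response rate by at most 1/154 = 0.65 points. The effect on power is negligible.

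**The case against.** The strongest reply is that the main body already settles the matter. The rule for early drug stops is stated in 3.3.1.2 and repeated in 3.1 and SAP 2.2. Table 1 footnote b ties the end of investigations to withdrawn consent. Section 3.3.1.2 itself uses the study loosely where it means treatment, so a sensible site may read Appendix 8 as meaning study drug. This stands as a limit on likelihood: the loss arises only where the sentence is taken literally. It does not remove the contradiction.

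Nor need a literal reading lose the Week 28 result. Sections 3.1 and 3.3.1.1 strongly recommend an efficacy assessment for patients leaving early, at Week 28 or, under 3.1, at an early end-of-study visit before formal withdrawal. That visit includes an antibody sample (Appendix 10, 2.4), and adverse events already reported are followed under 6.10. This stands and is why the loss is partial.

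Three stronger readings are tempting, and the documents do not support them:

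- *The missing response becomes a treatment failure.* Section 8.8 illustrates treatment-related reasons by failure requiring new lymphoma therapy and death from progression. SAP 16.1.2 ties the rule to the start of new treatment. A patient withdrawn for infusion intolerance alone is not plainly in that class. Depending on how the reason is classified, the response could be set to non-response, multiply imputed or left unimputed.
- *The trial's power is at risk.* On the small assumed counts above, it barely moves.
- *Absence from the 3.3.1.1 list proves the instruction invalid.* Section 4.10.1 also removes a patient from the study after unblinding, a reason not on that list, so the list is not exhaustive. The conflict rests on 3.3.1.2, not on the list.

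**Conclusion.** The point holds as a wrong operational instruction of minor weight. Appendix 8 contradicts the follow-up rule stated in Protocol 3.1 and 3.3.1.2 and in SAP 2.2. If followed literally, it could cost 6 to 9 of 10 antibody samples per affected patient (5 to 8 with an exit visit), the later capture of adverse events including those of special interest, and possibly the Week 28 response. These losses would fall selectively on patients who reacted to the drug.

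The counts are per-patient maxima. They assume literal withdrawal on an infusion day between Day 1 and Day 22 and the Table 1 schedule. How many patients would be affected cannot be derived from the documents. The harm is informative loss of safety, immunogenicity and possibly response data. It is not loss of power, and it is not a demonstrated shift in the imputed primary endpoint.

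**What to change.** Reword the Appendix 8 sentence along these lines: *stop the infusion and discontinue the patient from study drug, with follow-up per Section 3.3.1.2, including when the stop occurs during the Day 1 infusion.* The last clause closes the gap left by the wording of Table 1 footnote c.

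The cost is one sentence in a protocol amendment. Every visit, scan and sample involved is already scheduled, and the analysis and sample size do not change.
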